2.1.2.7.2 Lymphopenia

2.1.2.7.3 Asymptomatic hyperuricemia, hypophosphatemia, or creatine kinase (CK) elevations

2.1.2.7.4 Direct manifestations of KS

2.1.2.7.5 Direct manifestations of HIV infection, except for neurologic or cardiac manifestations

2.1.2.7.6 Direct manifestations of HIV therapy, except for neurologic or cardiac manifestations.

2.1.2.8 History of venous or arterial thromboembolism, *unless*:

2.1.2.8.1 Line-related thrombosis without embolus occurring ≥ 1 year prior to screening.

2.1.2.8.2 Complications resulting from atherosclerotic coronary artery disease, peripheral vascular disease, or cerebrovascular disease (including infarction) are not considered exclusion criteria unless in the opinion of the Principal Investigator or Lead Associate Investigator their clinical consequences in a particular subject places the subject at unacceptable risk if they were to participate in the study or confounds the ability to interpret data from the study.

2.1.2.9 Known drug-related, inherited, or acquired procoagulant disorder including prothrombin gene mutation 20210, antithrombin III deficiency, protein C deficiency, protein S deficiency and antiphospholipid syndrome but *not* including heterozygosity for the Factor V Leiden mutation or the presence of a lupus anticoagulant in the absence of other criteria for the antiphospholipid syndrome.

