2.1.2.5.2 Completely resected basal cell carcinoma *or*

2.1.2.5.3 *In situ* squamous cell carcinoma of the cervix or anus.

2.1.2.6 History of infection meeting any of the following criteria:

2.1.2.6.1 Any infection that would be scored as grade 4 by CTCAE that occurred *within six weeks* of study screening.

2.1.2.6.2 Any infection that would be scored as grade 3 by CTCAE that occurred *within two weeks* of study screening.

2.1.2.6.3 History of fungal and mycobacterial infections, unless *at least six weeks* has passed since the completion of induction antimicrobial therapy. Patients may be receiving consolidation therapy for infections of these types.

2.1.2.7 Any abnormality that would be scored as a \geq grade 3 toxicity by CTCAE, *except*:

2.1.2.7.1 Obesity is not considered an abnormality for the purposes of eligibility assessment unless in the opinion of the Principal Investigator or Lead Associate Investigator its clinical consequences in a particular subject places the subject at unacceptable risk if they were to participate in the study or confounds the ability to interpret data from the study.

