3.3 DOSE MODIFICATIONS

All treatment modifications should be discussed with the senior clinical investigators on the study. Dose modification guidelines apply to the Phase 1 and Phase 2 portions of the study as well as the Second Optional Course of Therapy.

For Phase 1: Subjects who are enrolled on the initial (5mg) dose level who experience a DLT *not including a thromboembolic event* that resolves to grade 1 (or the grade they had at entry) *within*

28 days and continue to have KS may be considered for further therapy at the 3mg dose level if they continue to have KS requiring therapy. Response assessment for any such patients is described in Section **10.4**.

Table 1: Dose Modification of Pomalidomide

Event	Action	Resumption of Therapy
Neutropenia. ANC 500 to <1000 cells/mm ³ (CTCAE Grade 3)	*If observed during cycle (day 2 of cycle onward) therapy may continue with additional weekly CBCs. If observed day 1 of new cycle , therapy should be held. Consider G-CSF. (filgrastim) 5mcg/kg/daily SC rounded by $\pm 10\%$ to use the most economical combination of available products (commercial vials contain 300 mcg or 480 mcg). Pegylated filgrastim should not be used. Pomalidomide should not be administered during G-CSF treatment or within 24 hours after a G-CSF dose.	CBCs should be evaluated weekly and a new cycle of treatment may commence at the same dose level on or after day 29 once ANC ≥ 1000 cells/mm ³ .
Neutropenia. ANC <500 cells/mm ³ . (CTCAE Grade 4)	*Suspend or hold pomalidomide. Administer G-CSF (filgrastim) 5mcg/kg/daily SC rounded by $\pm 10\%$ to use the most economical combination of available products (commercial vials contain 300 mcg or 480 mcg). Pegylated filgrastim should not be used. Pomalidomide should not be administered during G-CSF treatment or within 24 hours after a G-CSF dose.	CBCs should be evaluated weekly and a new cycle of treatment may commence at the same dose level on or after day 29 once ANC ≥ 1000 cells/mm ³ so long as criteria for a DLT are not met.

Event	Action	Resumption of Therapy

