Infection at any site (\geq CTCAE Grade 3) at least possibly attributable to pomalidomide	Suspend or hold Pomalidomide.	On or after day 29 and following documentation of resolution to \leq CTCAE Grade 1 at the same dose level. Therapy may resume during oral antibiotic consolidation therapy if there is no clinical or laboratory evidence of active infection.
CK elevation at least possibly attributable to pomalidomide (\geq CTCAE Grade 3)	Hold pomalidomide for a maximum of 2 weeks. Encourage increased oral fluid intake and avoidance of strenuous physical activities. Administer intravenous fluid if CK $>10,000$ U/L.	Resume therapy at the same dose level once resolution to \leq CTCAE Grade 2. Permanently discontinue if not at \leq CTCAE Grade 2 after a total of 3 weeks off drug (including the time off drug during the last week of the cycle) or if CK rises again to grade 4 and it is not possibly attributable to excess exercise or to trauma.
Any other DLT of CTCAE Grade 3 at least possibly attributable to pomalidomide	Suspend or hold pomalidomide.	On or after day 29 and following resolution to \leq CTCAE Grade 1 at the same dose level (see Section 3.5).

Event	Action	Resumption of Therapy
Any other DLT of CTCAE Grade 4 at least possibly attributable to pomalidomide	Discontinue therapy.	Not to resume (see section 3.3).

*At the discretion of the investigators, subjects who experience grade 3 or 4 neutropenia requiring G-CSF during a cycle as described below may receive G-CSF 5mcg/kg/daily SC rounded by $\pm 10\%$ to use the most economical combination of available products during the 'rest' days of subsequent cycles to minimize recurrent neutropenia.

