3.6 CRITERIA FOR REMOVAL FROM PROTOCOL THERAPY AND OFF STUDY CRITERIA

Prior to removal from study, effort must be made to have all subjects complete a safety visit approximately 28 days (± 7 days) following the last dose of therapy.

3.6.1 *Off-Therapy*

- 3.6.1.1 Any toxicity which is grade 4 and a dose limiting toxicity as defined in Section [3.1.2](#) at least possibly related to pomalidomide.
- 3.6.1.2 Any toxicity which is grade 3 and a dose limiting toxicity as defined in Section [3.1.2](#) at least possibly related to pomalidomide that does not resolve within 28 days to either grade 1 or the grade the patient had at entry.

- 3.6.1.3 Development of deep venous or arterial thrombosis, whether symptomatic or not, or development of a second on-study superficial venous thrombosis.
- 3.6.1.4 Pregnancy.
- 3.6.1.5 Achievement of pathologically confirmed complete remission.
- 3.6.1.6 Completion of six cycles of therapy (unless continuing to derive clinical benefit, as described in Section 3.1.4, in which case up to 12 cycles may be administered).
- 3.6.1.7 Clinically significant progressive disease compared with the tumor baseline for the current course of therapy by NCI-HAMB modified ACTG KS response criteria, sustained for eight weeks and not attributed to immune reconstitution syndrome. As KS may wax and wane, and improvements may be seen despite an initial period of progression, physician investigators may continue therapy through the first 6 cycles, despite meeting formal criteria for progressive disease, as long as disease progression is not clinically significant. Such cases must be discussed with the Principal Investigator and study subject. Clinically significant progression includes all symptomatic visceral disease and disease which is organ- or life-threatening.
- 3.6.1.8 ECOG performance status ≥ 3 .
- 3.6.1.9 Significant non-adherence to protocol therapy or HAART (the latter only in subjects with HIV-associated KS).
- 3.6.1.10 Inability to achieve HIV viral control, defined as failure to maintain an HIV VL $<10,000$ copies/mL persisting on at least two successive determinations at least four weeks apart and persisting despite optimization of HAART regimen. If a change in HAART regimen is required, a further period of up to eight weeks to assess the effect of this change on HIV VL is allowable.
- 3.6.1.11 Subject requests to be withdrawn from active therapy

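### Table 1 and Section 3.6.1.2 set different recovery standards for a grade 3 DLT, leaving a grade 2 entrant who returns to grade 2 with no rule for resuming or stopping; the Table 1 CK row is also out of step with eligibility

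*Combined protocol and SAP*

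**What the plan says.** **Eligibility.** Exclusion 2.1.2.7 covers "Any abnormality that would be scored as a" grade 3 or higher toxicity, with listed exceptions. One exception, 2.1.2.7.3, is "Asymptomatic hyperuricemia, hypophosphatemia, or creatine kinase (CK) elevations". Grade 2 abnormalities are outside this exclusion altogether.

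**Off-therapy rule, all parts of the study.** Section 3.6.1.2 removes a subject for a grade 3 DLT at least possibly related to pomalidomide "that does not resolve within 28 days to either grade 1 or the grade the patient had at entry".

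**Table 1, row for other grade 3 DLTs.** Drug is held. Resumption is "On or after day 29 and following resolution to" grade 1 or lower, at the same dose level. The row then refers the reader to Section 3.5.

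**Section 3.3 text, Phase 1 only.** A subject at 5mg whose non-thromboembolic DLT "resolves to grade 1 (or the grade they had at entry") within 28 days may be considered for further therapy at 3mg.

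**Table 1, CK row (grade 3 or higher, at least possibly drug-related).** Drug is held for at most 2 weeks. The instruction is "Resume therapy at the same dose level once resolution to" grade 2 or lower, with permanent discontinuation if that is not reached "after a total of 3 weeks off drug (including the time off drug during the last week of the cycle").

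Section 3.3 applies the dose modification guidelines to Phase 1, Phase 2 and the optional second course.

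**The concern.** Two sections treat a return to the entry grade as recovery, and the table that governs resumption does not. For a subject who entered with a grade 2 abnormality, one section says the toxicity has resolved well enough to stay on therapy, while the other says it has not resolved well enough to take the drug. Two investigators could handle the same event differently, each following the text.

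The choice matters beyond the individual. Sections 3.1.4 and 6.2 count only subjects who complete at least two cycles as evaluable for response. The replacement provision in 3.1.4 covers only removals for reasons other than drug toxicity. Whether a subject held early may resume can therefore decide whether that subject enters the response set.

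The CK row raises a related question: eligibility accepts a CK grade that the table does not accept as recovery.

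**Working it through.** No calculated figure in the plan is involved. The check follows defined cases through the rules.

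**Case A: other grade 3 DLT, Phase 2 or second course.**
1. The subject enters with a grade 2 abnormality. 2.1.2.7 does not exclude it. The specific laboratory limits in 2.1.1.8 and 2.1.1.9, or investigator judgement under 2.1.2.14, could still do so.
2. On drug it becomes grade 3, is at least possibly due to pomalidomide, is a DLT under 3.1.2.3, and has no Table 1 row of its own. Table 1 orders a hold.
3. Within 28 days it is back at grade 2.
4. Section 3.6.1.2: the entry grade has been reached, so the criterion for removal is not met.
5. Table 1: grade 2 is above grade 1, so resumption is not allowed.
6. The Section 3.3 concession does not apply, because it is limited to Phase 1. Section 3.6.1.12 lets the Principal Investigator remove the subject but does not authorise resumption.

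Result: no toxicity rule ends the hold in either direction. For entry at grade 0 or 1 the standards agree, since recovery under 3.6.1.2 then also means grade 1 or lower. The conflict needs an entry grade above 1.

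**Case B: the same event in Phase 1 at 5mg.**

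| | Recovery needed | Dose on resumption |
|---|---|---|
| Section 3.3 text | grade 1 or entry grade, within 28 days | 3mg may be considered |
| Table 1 row | grade 1 or lower | same dose level |

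The two differ on both points. Section 3.1.5 reports that the first six patients completed 8 weeks without a DLT by 06/28/2012, so the Phase 1 text has little practical role now, but it remains in the current version.

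**Case C: CK.**
1. The subject enters with asymptomatic grade 3 CK, which 2.1.2.7.3 permits.
2. On drug CK rises further and the rise is judged at least possibly drug-related. Table 1 orders a hold.
3. CK returns to grade 3, the admitted grade. This is not grade 2 or lower, so drug may not resume.
4. After 3 weeks off drug (2-week hold + 1-week rest = 3 weeks, or 21 days) Table 1 requires permanent discontinuation.
5. Section 3.6.1.2 gives no relief. It covers only toxicities that are both grade 3 and a DLT, and 3.1.2.3.1 carves CK out of the grade 3 DLT rule. If the rise is a grade 4 DLT, 3.6.1.1 takes the subject off therapy whatever the recovery.

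Result: the outcome is determinate (off therapy), but it is reached at a CK grade that eligibility accepts.

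**Blood-count rows.** Resumption thresholds against entry minima: ANC 1000 against 1000; platelets 50,000 against 75,000; hemoglobin 10.0 (unit printed as g/L in Table 1) against 10 g/dL. Reading the hemoglobin unit as g/dL, a subject back at the entry minimum meets each threshold, so these rows do not share the problem.

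**Cross-reference.** Section 3.5 is Cost and Compensation. The off-therapy criteria are in Section 3.6, so the pointer does not lead to the entry-grade rule.

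**The case against.** The strongest reply is that the two rules do different jobs. Table 1 says when drug may restart and 3.6.1.2 says when the subject must leave, so a stricter threshold for restarting is not in itself a contradiction. Section 3.3 also calls its rules guidelines and wants modifications discussed with senior investigators, and 3.6.1.12 always allows removal. Part of this stands: nobody is trapped on the study. It does not close the gap. For a grade 2 entrant the table requires a state better than at entry, sets no limit on the wait in that row, and leaves the entry-grade wording in 3.6.1.2 with no route back to drug.

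Four stronger readings are tempting, and the documents do not support them.
- A reader might infer that the CK subject is also left between rules. Table 1 orders discontinuation, so this subject is off therapy. The row also needs attribution to pomalidomide, so an unchanged entry value judged unrelated does not trigger it.
- A reader might infer that Section 3.3 sets a general entry-grade standard. It is limited to Phase 1, where it supplies a route at 3mg.
- A reader might count each affected subject as a loss of one in 10 or one in 15. Those are targets of evaluable subjects. Someone who does not complete two cycles was never in them, and Section 10.3 sets the ceiling of 40 to allow for inevaluable subjects. Section 10.4 also says the fifteen evaluable HIV-positive subjects were already accrued by amendment G.
- A reader might infer that tolerability is recorded as worse than it was. A DLT is counted when it occurs, whatever is later decided about resumption, and the row for other grade 3 DLTs orders a hold, not removal.

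**Conclusion.** The contradiction between the Table 1 row for other grade 3 DLTs and Section 3.6.1.2 holds, and it decides whether a subject in Phase 2 or the second course may resume drug. For Phase 1 the same row also disagrees with the Section 3.3 text on recovery standard and dose level. The pointer to Section 3.5 is wrong. The CK row is a separate mismatch with 2.1.2.7.3, with a determinate outcome that 3.6.1.2 does not touch.

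The point is minor and its size is unknown: the documents do not say how many subjects enter with a grade 2 abnormality or with CK of grade 3 or higher, or how often these worsen on drug. The conclusion assumes that the entry abnormality passes the specific laboratory limits and investigator judgement, and that the on-study event is attributed at least possibly to pomalidomide. It takes no position on which recovery standard is clinically right.

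**What to change.** Reconcile Table 1 (the rows for other grade 3 DLTs and for CK), the Section 3.3 Phase 1 text, Section 3.6.1.2 and exclusion 2.1.2.7.3 to one recovery standard, chosen by the clinical team. Whatever is chosen, the text should say what happens to a subject who is back at the entry grade but above the table's threshold. Change the pointer in the row for other grade 3 DLTs from Section 3.5 to Section 3.6.

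Record the entry grade beside each on-study grade, so that the rule can be applied and any hold or discontinuation read against it. Section 3.6.1.2 already needs the entry grade, and screening and baseline evaluations supply the history and laboratory values, CK included.

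The cost is a wording amendment and one added data item. No sample size, analysis or visit changes.

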2.1.2.10 Pregnancy

- 2.1.2.11 Breast feeding (if lactating, must agree not to breast feed while taking pomalidomide).
- 2.1.2.12 Prior therapy with pomalidomide.
- 2.1.2.13 Known hypersensitivity to thalidomide, lenalidomide or pomalidomide. including prior development of erythema nodosum if characterized by a desquamating rash while taking thalidomide, lenalidomide or pomalidomide.
- 2.1.2.14 Any condition, including the presence of laboratory abnormalities, which in the opinion of the Principal Investigator or Lead Associate Investigator places the subject at unacceptable risk if they were to participate in the study or confounds the ability to interpret data from the study.

2.2 RESEARCH ELIGIBILITY EVALUATION

Potential subjects will be evaluated by a HAMB physician investigator for protocol eligibility. Baseline evaluation will include a complete medical history, review of systems, and physical examination including documentation of the presence and extent of any KS lesions.

2.2.1 Clinical Examination

- 2.2.1.1 Complete medical history
- 2.2.1.2 Comprehensive physical examination.

2.2.2 Clinical Laboratory Data

(studies performed in Clinical Center Department of Laboratory Medicine except HIV, HBV and HCV viral load monitoring performed in Clinical Center Blood Bank)

- 2.2.2.1 CBC with differential and reticulocyte count
- 2.2.2.2 Acute care panel (Sodium, Potassium, Chloride, CO₂, Creatinine, Glucose, and Urea Nitrogen)
- 2.2.2.3 Mineral panel (Phosphorus, Magnesium, Albumin, and Calcium)
- 2.2.2.4 Hepatic panel (Alkaline Phosphatase, ALT, AST, Total Bilirubin, and Direct Bilirubin)
- 2.2.2.5 C-reactive protein
- 2.2.2.6 Creatine kinase, uric acid, LDH, amylase and lipase
- 2.2.2.7 APTT, PT, thrombin time (TT), fibrinogen, D-dimer
- 2.2.2.8 Lymphocyte phenotype TBNK (requires simultaneous CBC and automated differential)
- 2.2.2.9 HIV Western blot (unless prior lab evaluation by Department of Laboratory Medicine, Clinical Center, NIH shows that the patient is HIV infected)
- 2.2.2.10 HIV viral load if HIV seropositive by Western Blot
- 2.2.2.11 RPR
- 2.2.2.12 Tuberculosis testing by PPD or interferon gamma release assay (Quantiferon Gold)
- 2.2.2.13 Urinalysis.

2.2.3 Pregnancy Testing

- 2.2.3.1 Urine and serum β-hCG (female subjects only). Must follow pregnancy testing requirements as outlined in the POMALYST REMS™ program.

2.2.4 Radiographic studies

- 2.2.4.1 Chest X-ray.
- 2.2.4.2 If clinically indicated, a Chest CT may be performed where necessary to assess abnormal chest x-ray findings or unexplained respiratory symptoms.
- 2.2.4.3 Endoscopic studies may be performed when clinically indicated to evaluate and measure visceral KS. Such studies are indicated where there are symptoms suggestive of KS involvement at the site (including but not limited to hemoptysis, melena, unexplained dyspnea) and/or findings on Chest CXR or computer tomography which could represent visceral KS. Studies may include bronchoscopy, upper and/or lower gastrointestinal endoscopy. Evaluation is not required in the absence of symptoms or imaging abnormalities.

2.2.5 KS Tumor Biopsy

- 2.2.5.1 Where pathological tissue for confirmation of the diagnosis has not already been obtained, biopsy of skin or other involved tissue will be performed.
- 2.2.5.2 Where diagnostic biopsies are obtained, the specimens will be handled as follows:
 - 2.2.5.2.1 Place sufficient tissue for diagnostic purposes directly into formalin and submit to Laboratory of Pathology for histopathology and immunohistochemistry including KSHV-LANA and KSHV-vIL-6.
 - 2.2.5.2.2 Additional research tests may be performed on the screening tissue biopsy *only* where the patient has enrolled on study 01-C-0038 (Collection of Blood, Bone Marrow, Tumor, or Tissue Samples from Patients with HIV Infection, KSHV Infection, Viral-related Pre-Malignant Lesions, and/or Cancer). See Section **5.1.2.3.1** for handling and prioritization instructions.

2.3 PARTICIPANT REGISTRATION AND STATUS UPDATE PROCEDURES

Registration and status updates (e.g., when a participant is taken off protocol therapy and when a participant is taken off-study) will take place per CCR SOP ADCR-2, CCR Participant Registration & Status Updates found [here](#).

[figure not shown]
3 STUDY IMPLEMENTATION

3.1 STUDY DESIGN

This is an open label single agent study of pomalidomide in patients with KS, whether HIV associated or not.

3.1.1 Study Schema

Phase I Dose-establishment component:

[figure not shown]

*Expansion cohort accrual goals will be 15 evaluable HIV positive and 10 evaluable HIV negative patients

For patients with HIV-associated KS, dose expansion cohort requires additional eligibility criteria

(stable disease despite 3 months of cART or progression despite 2 months of cART)

Phase II Antitumor activity assessment component

*Guidelines for duration of therapy in the antitumor assessment phase are given in S3.1.4

Eligibility criteria for optional second treatment course are given in S3.1.6.

Schedule of visits and duration of long term follow up are given in S3.4.3.6

3.1.2 Dose Limiting Toxicity

For purposes of defining the toxic dose and as a basis of discussion for off-study criteria, the following is the definition of dose-limiting toxicity (DLT). It should be noted that neither pre-existing manifestations of HIV infection, nor of therapy for HIV infection, nor of KS (including bleeding from KS) will be considered dose-limiting. Dose limiting toxicities will be assessed over the first 8 weeks (2 cycles) of drug administration.

If a patient meets the criteria defined below, they will be considered as having dose-limiting toxicity.

- 3.1.2.1 Any grade 4 toxicity not including lymphopenia, CD4 lymphopenia, neutropenia, anemia and bilirubin or CK elevation that is at least possibly due to pomalidomide and is not attributable to HIV, its therapy or KS.
- 3.1.2.2 For lymphopenia, CD4 lymphopenia, neutropenia, or anemia and bilirubin or CK elevation additional restrictions apply to better separate drug effects from manifestations of HIV and/or its therapy. For these parameters, the definition of dose-limiting toxicity is as follows:
 - 3.1.2.2.1 For lymphopenia and CD4 counts, a decrease that (1) represents a grade 4 toxicity; (2) represents a 80% decrease from the entry value; (3) occurs in a patient with controlled HIV (<1,000 copies/mL); **and** (4) represents a 50 cell/mm³ decrease from entry will be considered dose-limiting if found to be present on two successive determinations. If a CD4 count meets the numerical criteria on one determination, it should be repeated at the next possible visit to see if it is confirmed.
 - 3.1.2.2.2 Neutropenia will only be considered dose-limiting if grade 4 for 14 days or more (including with G-CSF administration) or if grade 4 febrile neutropenia occurs.
 - 3.1.2.2.3 Anemia will only be considered dose limiting if grade 4 and other causes are not identified (for example, antiretroviral therapy with agents such as zidovudine).

- 3.1.2.2.4 For patients on HIV protease inhibitors who manifest hyperbilirubinemia, an increase total bilirubin of ≥ 5.0 mg/mL over baseline with an increase in indirect bilirubin of ≥ 4.5 mg/ml over baseline is considered dose-limiting. This is because bilirubin is frequently elevated in patients receiving these medications. This does not apply to patients whose HAART regimen does not include a protease inhibitor.
- 3.1.2.2.5 Grade 4 creatine kinase (CK) elevations will not be considered dose-limiting if it is determined that this is at least possibly due to recent exercise or trauma. This is because it is our experience that some KS patients and HIV-infected patients on clinical trials develop substantially increased CK levels from exercise or trauma.
- 3.1.2.3 **Any grade 3 toxicity** that is at least possibly due to pomalidomide and is not attributable to HIV, its therapy, or KS with the following restrictions:
 - 3.1.2.3.1 Those toxicities excluded above in section **3.1.2.2**
 - 3.1.2.3.2 Grade 3 thrombocytopenia will only be considered dose limiting if grade 3 for 14 days or more (all grade 4 thrombocytopenia will be considered dose limiting).
 - 3.1.2.3.3 Grade 3 asymptomatic hyperuricemia or hypophosphatemia will not be considered dose limiting, as these are often caused by HIV infection or antiretroviral therapy.
 - 3.1.2.3.4 Grade 3 amylase elevations will not be considered dose-limiting if it is determined that it is not of pancreatic origin.
 - 3.1.2.3.5 For rash, grade 3 toxicity is considered dose-limiting only if it does not decrease to grade 1 within 4 weeks off therapy; if it recurs on re-challenge with pomalidomide; or if it is erythema nodosum characterized by a desquamating rash.
 - 3.1.2.3.6 For hypertension, grade 3 toxicity is considered dose limiting where systolic blood pressure of ≥ 160 mm Hg or diastolic blood pressure of ≥ 100 mm Hg is not controlled with antihypertensive medications (all grade 4 hypertension will be considered dose limiting).
- 3.1.2.4 Any arterial or deep venous thrombembolic event or a second superficial thromboembolic event that is at least possibly due to pomalidomide.
- 3.1.2.5 Inability to deliver pomalidomide on at least 50% of scheduled days during the first two cycles of therapy as a result of toxicity that is probably or definitely attributable to pomalidomide will be considered dose limiting. Delivery interruptions not related to pomalidomide (for example, due to unrelated intercurrent illness, patient personal emergencies, or other exigencies) will not be considered for this criterion.

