2 ELIGIBILITY ASSESSMENT AND ENROLLMENT

2.1 ELIGIBILITY CRITERIA

2.1.1 *Inclusion Criteria*

- 2.1.1.1 Age \geq 18 Years.
- 2.1.1.2 Any HIV status.
- 2.1.1.3 Kaposi sarcoma pathologically confirmed by Department of Pathology, Clinical Center, National Institutes of Health.
- 2.1.1.4 At least five measurable KS lesions with no previous local radiation, surgical or intralesional cytotoxic therapy that would prevent response assessment for that lesion.
- 2.1.1.5 ECOG Performance Status \leq 2
- 2.1.1.6 Life expectancy \geq 6 months
- 2.1.1.7 For patients with HIV-associated KS:
 - 2.1.1.7.1 Must be receiving, and adherent to, a HAART regimen consistent with current clinical guidelines.
 - 2.1.1.7.2 Must have been receiving HAART for at least one month.
 - 2.1.1.7.3 Must have achieved an HIV VL $<10,000$ copies/mL.
- 2.1.1.8 The following hematological parameters:
 - 2.1.1.8.1 Hemoglobin \geq 10 g/dL
 - 2.1.1.8.2 Platelets \geq 75,000 cells/mm³
 - 2.1.1.8.3 Absolute neutrophil count (ANC) \geq 1000 cells/mm³
- 2.1.1.9 The following biochemical parameters:
 - 2.1.1.9.1 Estimated or measured creatinine clearance \geq 45mL/minute (see [Appendix 9](#) for estimation of creatinine clearance)
 - 2.1.1.9.2 Serum alanine aminotransferase (ALT) \leq 2.5 x upper limit of normal

- 2.1.1.9.3 Serum aspartate aminotransferase (AST) $\leq 2.5 \times$ upper limit of normal
- 2.1.1.9.4 Bilirubin $\leq 1.5 \times$ upper limit of normal unless the patient is receiving protease inhibitor therapy (e.g. indinavir, ritonavir, nelfinavir, or atazanavir) known to be associated with increased bilirubin, in which case total bilirubin $\leq 7.5 \text{ mg/dL}$ with direct fraction $\leq 0.7 \text{ mg/dL}$.

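### The bilirubin DLT thresholds for patients on protease inhibitors are printed in mg/mL instead of mg/dL, so the criterion could never trigger if applied literally

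*Combined protocol and SAP*

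**What the plan says.** Section 3.1.2 sets general DLT rules and then treats some laboratory parameters separately.

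- **3.1.2.1 (grade 4 rule)** covers "Any grade 4 toxicity not including lymphopenia, CD4 lymphopenia, neutropenia, anemia and bilirubin or CK elevation", subject to attribution.
- **3.1.2.2** says that for the parameters set aside, "additional restrictions apply to better separate drug effects from manifestations of HIV and/or its therapy", and continues: "For these parameters, the definition of dose-limiting toxicity is as follows".
- **3.1.2.2.4**, the only bilirubin item in that list, concerns patients on HIV protease inhibitors with hyperbilirubinemia. It makes dose-limiting "an increase total bilirubin of ≥ 5.0 mg/mL over baseline with an increase in indirect bilirubin of ≥ 4.5 mg/ml over baseline". The reason given is that these drugs often raise bilirubin. It closes: "This does not apply to patients whose HAART regimen does not include a protease inhibitor".
- **3.1.2.3.1** exempts from the grade 3 rule "Those toxicities excluded above in section" 3.1.2.2.

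The entry criterion 2.1.1.9.4 uses a different unit. For patients on protease inhibitors "known to be associated with increased bilirubin, in which case total bilirubin" may be at most 7.5 mg/dL, with a direct fraction of at most 0.7 mg/dL.

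**The concern.** The two thresholds in 3.1.2.2.4 are the only numeric bilirubin limits in the DLT definition. For a patient on a protease inhibitor, bilirubin is taken out of the general grade 4 rule by 3.1.2.1 and out of the grade 3 rule by 3.1.2.3.1. That leaves 3.1.2.2.4 as the sole bilirubin-specific criterion. If its unit is wrong by a factor of 100, these patients have no working bilirubin DLT in print.

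The definition is used in several places:

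- Section 3.1.3 calls a dose toxic when two or more subjects at that level have a DLT in the first 8 weeks.
- Off-therapy rules 3.6.1.1 and 3.6.1.2 act on grade 4 DLTs and on unresolved grade 3 DLTs.
- Table 1 has no bilirubin row, so bilirubin falls to its two rows for any other DLT. Section 3.3 applies the table to Phase 1, Phase 2 and the second course.

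The use of the definition therefore did not end with the dose decision.

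**Working it through.** **Inputs**

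- Printed thresholds (3.1.2.2.4): rise in total bilirubin of at least 5.0 mg/mL, with rise in indirect bilirubin of at least 4.5 mg/mL.
- Entry cap for the same patients (2.1.1.9.4): total bilirubin 7.5 mg/dL.
- Dose rule (3.1.3): toxic at two or more DLTs. Recorded result (3.1.5): none in the first six patients.

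**Unit conversion** (1 dL = 100 mL, so mg/dL = mg/mL × 100)

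- Total: 5.0 × 100 = 500 mg/dL; 500 / 7.5 = 66.7 times the cap.
- Indirect: 4.5 × 100 = 450 mg/dL; 450 / 7.5 = 60 times the same total-bilirubin cap.
- Read as mg/dL: 5.0 / 7.5 = 0.67 of the cap, which is on the scale of the entry criterion.

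Both conditions must hold together, and both carry the wrong unit.

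**Effect on the dose decision**

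With 0 DLTs recorded in six and a limit of two, at least 2 of the 6 subjects would have to be reclassified before the 5 mg dose would count as toxic.

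**Size of the look-back** (scheduled post-baseline hepatic panels; two 28-day cycles = days 1 to 56)

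- Under 3.4.4.3 (extra checks on day 15 only): cycle 1 day 15, cycle 2 day 1, cycle 2 day 15 = 3 per subject.
- Under footnote 3 of the calendar in 3.4.1 (days 8, 15 and 22 of cycle 1): add cycle 1 days 8 and 22 = 5 per subject. This assumes that those checks include the hepatic panel listed in 3.4.4.3.
- Cycle 3 day 1 is study day 2 × 28 + 1 = 57, just past the window. Section 3.4.4.2.1 allows the draw on or immediately before day 1, so this panel is borderline.
- Upper limit, if all six subjects were on a protease inhibitor: 6 × 3 = 18 to 6 × 5 = 30 panels, plus up to 6 borderline draws. The documents do not say how many of the six were.

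**The case against.** **The slip corrects itself.** Section 2.1.1.9.4 gives bilirubin for the same patients in mg/dL, and a clinician could hardly take 5.0 to mean 500 mg/dL. The documents show nobody applying the printed unit. This is a good reason to expect that no harm was done. It is not a reason to leave an operative safety threshold wrong in print in both of its parts.

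**The main use is over, and other safeguards exist.** The Phase I decision closed with no DLTs in six. Treatment modifications are discussed with senior investigators (3.3), the team reviews adverse events weekly (6.3, 7.4.1), and the Principal Investigator may stop therapy (3.6.1.12). Section 3.1.2.5 makes failure to deliver half the scheduled doses because of toxicity a DLT in its own right. All of this stands and limits the weight of the point. However, 3.1.2.5 covers only the first two cycles and requires probable or definite attribution, and discretion is not a threshold.

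**A stronger reading: no bilirubin DLT for anyone else.** A reader might infer that patients not on a protease inhibitor, including HIV-negative patients, have no bilirubin DLT. On that view 3.1.2.1 removes bilirubin for everyone, 3.1.2.2 presents its list as the definition, and 3.1.2.3.1 closes the grade 3 route. The text does not support this as the natural reading. The list is introduced as extra restrictions to separate drug effects from HIV and its therapy, and the reason in 3.1.2.2.4 concerns protease inhibitors only. The item says that it does not apply to regimens without one, so for those patients it excludes nothing. The parallel CK item, "Grade 4 creatine kinase (CK) elevations will not be considered dose-limiting if it is determined" to be possibly due to exercise or trauma, makes sense only if the general rule otherwise stands. What remains is a drafting gap: no sentence says outright that the general rules return.

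**Conclusion.** The unit in 3.1.2.2.4 is wrong as written. The printed thresholds equal 500 and 450 mg/dL, 66.7 and 60 times the 7.5 mg/dL entry cap, and cannot be met in practice. That mg/dL was meant is an inference from 2.1.1.9.4, but a secure one. That the criterion would never trigger holds only if the printed unit is applied literally.

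A reader might go further and infer that a DLT was missed, or that 5 mg was wrongly declared tolerable. The documents do not support that. They report no DLTs in six subjects, report no bilirubin values, and do not say how many subjects took a protease inhibitor. Two reclassifications would be needed to change the decision. No sample size, power or error rate depends on this threshold.

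The rule for patients not on a protease inhibitor needs at most a clarification. Similar unit slips for hemoglobin are clerical: Table 1 prints 10.0 g/L twice and 4.2.3 prints 8.0 mg/dL. The same Table 1 row gives 8.0 g/dL and the entry criterion gives 10 g/dL, so the meaning is plain.

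**What to change.** 1. In 3.1.2.2.4, change mg/mL to mg/dL for both the total and the indirect threshold.
2. Confirm that bilirubin values already collected for any of the six Phase I subjects on a protease inhibitor were judged in mg/dL. This means 3 to 5 scheduled panels per subject within days 1 to 56, plus the cycle 3 day 1 draw.
3. Optional: add to 3.1.2.2.4 that for patients not on a protease inhibitor, including HIV-negative patients, the general rules in 3.1.2.1 and 3.1.2.3 apply to bilirubin. This writes down the natural reading, but it settles a rule and so should be adopted deliberately.
4. In passing, correct the hemoglobin units in Table 1 and 4.2.3 to g/dL.

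The cost is a short amendment, which under the Statement of Compliance needs IRB approval, and a review of results already on file. No new visits, samples or procedures are needed.
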